Methodology	
This is a three parallel group (A, B & C), open-label, non-randomized, multicenter study. All three groups will enroll independently.
 
Group A: will be composed of newly-diagnosed, elderly patients with IDH1^{R132H}-non mutant and MGMT promoter-unmethylated anaplastic astrocytoma or glioblastoma who will receive TG02 and radiation therapy.
 
Group B will be composed of newly-diagnosed, elderly patients with IDH1^{R132H}-non mutant and MGMT promoter-methylated anaplastic astrocytoma or glioblastoma who will receive TG02 and temozolomide.
 
For both Groups A and B, there will be a classical 3+3 dose escalation and an expansion phase with stopping rules in the study.
 
Group C patients will be composed of patients initially diagnosed with IDH1^{R132H}-non-mutant anaplastic astrocytoma or glioblastoma at first relapse post TMZ/RT → TMZ therapy who will receive TG02.
 
All patients will receive TG02 until disease progression, unacceptable toxicity or up to 12 cycles. [Upon completion of 12 cycles without disease progression

	or unacceptable toxicity, patients may continue on TG02 as determined by the Investigator.]

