Treatment Test product, dose and mode of administration Duration of treatment	
TG02 can be started on the day of enrollment.
 
Group A:
 
Patients with MGMT promoter-unmethylated tumors will receive TG02 (initial dose of 100 mg) orally twice weekly (days 1, 4, 8, 11, 15 and 18) in combination with standard involved-field hypofractionated RT (40 Gy in 15 fractions of 2.66 Gy) for 3 weeks (days 1-21). TG02 should be taken approximately one hour prior to RT.
 
Seven days after completing combination therapy, patients will receive maintenance cycles of single agent TG02 until disease progression, unacceptable toxicity or up to 12 months. TG02 will be administered on days 1, 4, 8, 11, 15, 18, 22 and 25 of each 28-day maintenance cycle. [Upon completion of 12 cycles without disease progression or unacceptable toxicity, patients may continue on TG02 as determined by the Investigator.]
 
Group B:
 
Patients with MGMT promoter-methylated tumors will receive TG02 (initial dose of 100 mg) orally twice weekly with temozolamide. TG02 will be taken on days -7, -4, 1, 4, 22 and 25 in cycle 1. As of cycle 2, TG02 is given on days 1, 4, 22 and 25 of a 28-day cycle. TMZ will be given in the standard 28-day cycle regimen (200 mg/m²) for 5 days q 28 starting at Day 1. Combination therapy will continue until disease progression, unacceptable toxicity or up to 12 cycles. [Upon completion of 12 cycles without disease progression or

	
unacceptable toxicity, patients may continue on TG02 and TMZ or single agent TG02 as determined by the Investigator.]
 
Group C:
 
Patients will receive single agent TG02 at 150 mg orally twice weekly. TG02 will be administered on days 1, 4, 8, 11, 15, 18, 22 and 25. The lowest permitted dose will be 100 mg BIW Single agent therapy will continue until disease progression, unacceptable toxicity or up to 12 cycles. [Upon completion of 12 cycles without disease progression or unacceptable toxicity, patients may continue on TG02 and TMZ or single agent TG02 as determined by the Investigator.]

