2.1 General objectives

2.1.1 Main objective

Groups A and B: safety and tolerability

Group A: Establish the recommended phase II dose of TG02 in combination with radiotherapy (RT) to be used in further trials exploring the antitumor activity of TG02 in elderly patients with IDH1^{R132H}-non-mutant anaplastic astrocytoma or IDH1^{R132H}-non-mutant glioblastoma and unmethylated MGMT promoter.

Group B: Establish the recommended phase II dose of TG02 in combination with temozolomide (TMZ) to be used in further trials exploring the antitumor activity of TG02 in elderly patients with IDH1^{R132H}-non-mutant anaplastic astrocytoma or IDH1^{R132H}-non-mutant glioblastoma and methylated MGMT promoter.

Group C: explore single agent activity

Investigate if single agent TG02 demonstrates sufficient antitumor activity in IDH1^{R132H}-non-mutant anaplastic astrocytoma or IDH1^{R132H}-non-mutant glioblastoma at first relapse after initial treatment with TMZ/RT - TMZ to justify further development.

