4.3 Group C

AA and GBM patients at first relapse after TMZ/RT → TMZ therapy will receive single agent TG02 at 150 mg orally twice weekly. TG02 will be administered on days 1, 4, 8, 11, 15, 18, 22 and 25 of each 28-day cycle (Appendix H). Single agent therapy will continue until disease progression or for up to 12 cycles. Upon completion of 12 cycles without disease progression or unacceptable toxicity, patients may continue on TG02 as determined by the Investigator.

The lowest permitted dose will be 100 mg TG02 twice weekly.

An A'Hern one-stage design will be applied. Forty-five (45) eligible patients who started treatment will be evaluated for PFS at 6 months.

AA-Anaplastic Astrocytoma	d-Days
GBM-Glioblastoma	Q28q-cycle of 28 days
TMZ-Temozolamide	PD-progressive disease
RT-Radiation Therapy	

5 Therapeutic regimens, expected toxicity, dose modifications

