5.3 Treatment duration

Group A: combination treatment (TG02 and RT) will continue for 3 weeks. Maintenance cycles (TG02 single agent) will continue until disease progression or until the patient completes 12 cycles therapy.

Group B: combination treatment (TG02 and TMZ) will continue until disease progression or until the patient completes 12 cycles of therapy.

Group C: TG02 treatment will continue until disease progression or until the patients completes 12 cycles of therapy.

Treatment with TG02 may be continued beyond 12 cycles if there is no relevant toxicity, no progressive disease, and if the treating physician considers this to be of clinical benefit. The disease status will be regularly assessed according to the protocol during this period to evaluate the duration of response.

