5.6.1 Treatment of AA or GBM

The following treatments are **NOT** permitted during the study treatment:

- Treatment with other systemic anti-cancer agents before disease progression (chemotherapy, hormonal therapy, immunotherapy, anti-tumor vaccines, targeted agents, or other treatments not part of protocol-specified anti-cancer therapy)
- Concurrent investigational agents of any type before disease progression
- Craniotomy, intra-tumoral interstitial therapy, any surgical procedures under investigation or any form of radiosurgery

Any of the above will lead to patient's discontinuation from study treatment.

Alternative therapies are discouraged and must be discussed with the local investigator.

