7.2.2 Efficacy

To ensure a homogeneous radiological evaluation, all MRI images will be retrospectively centrally reviewed.

The following criteria will be used to determine the efficacy of study treatment.

Progression Free Survival (PFS): PFS is defined as the number of days from consent to the date of earliest disease progression based on Response Assessment in Neuro Oncology (RANO) criteria (as determined by the Investigator) or to the date of death, if disease progression does not occur. In group C, patients for whom neither death nor progression have been documented will be censored on the date of the last radiological assessment if they have no post anti-cancer therapy. If a patient has other post anti-cancer therapy prior to progression or death, the data will be censored at the date of last radiological assessment prior to or on the start date of post anti-cancer therapy. In group A and B, post anti-cancer therapy is not collected. The data will be censored at the date of the last radiological assessment. In all groups, if a patient with no post-baseline radiological assessment did not experience progression nor died, then the data will be censored at the date of enrollment.

PFS at 6 months (PFS-6) is the PFS rate at 6 months extracted from the PFS Kaplan Meier distribution based on RANO criteria (as determined by the Investigator)

Overall Survival (OS): OS is defined as the number of days from consent to the date of death due to any cause. If a patient has not died, the data will be censored at the last date documented to be alive.

OS at 9 months (OS-9) is the OS rate at 9 months extracted from the OS Kaplan Meier distribution.

Objective (ORR) and complete (CR) response rates are the proportions of patients with best overall response PR+CR or CR (see below) respectively.

Duration of objective (complete) response (DOR): DOR is determined as the number of days from the time point where the overall response PR or CR (CR) was first seen to the earliest date of detection of disease progression based on RANO criteria (as determined by the Investigator) or to the date of death, if disease progression does not occur. The same censoring rules defined above for PFS are applicable.

A success is defined as a patient achieving either confirmed CR or PR (> 4 week) or free of progression at 6 months.

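### Minor, wrong as written: the Group C synopsis carries over the Group B sentence and so permits TMZ with TG02 after cycle 12 in a single-agent arm

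*Combined protocol and SAP*

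**What the plan says.** The Treatment row of the protocol summary describes Group C as single-agent TG02 at 150 mg twice weekly. It then says that treatment continues "up to 12 cycles. [Upon completion of 12 cycles without disease progression or unacceptable toxicity, patients may continue on TG02 and TMZ" or on single-agent TG02, as the investigator decides. The Group B paragraph above it closes with the same permission.

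The other texts on Group C treatment after cycle 12 name TG02 only:

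- Protocol summary, Methodology row (all groups): without progression "or unacceptable toxicity, patients may continue on TG02 as determined by the Investigator".
- Section 4.3, Group C: "Upon completion of 12 cycles without disease progression or unacceptable toxicity, patients may continue on TG02 as determined by the Investigator".
- Section 5.3, all groups: "Treatment with TG02 may be continued beyond 12 cycles if there is no relevant toxicity", with further conditions on progression and clinical benefit.

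The Group C objective in section 2.1.1 is to "Investigate if single agent TG02 demonstrates sufficient antitumor activity". Section 5.6.1 prohibits "Treatment with other systemic anti-cancer agents before disease progression" during study treatment and takes a patient who receives them off study treatment. For Group C PFS, section 7.2.2 adds: "If a patient has other post anti-cancer therapy prior to progression or death, the data will be censored" at the last radiological assessment up to the start of that therapy.

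**The concern.** The sentence is a treatment permission, not background. A site working from the synopsis could add TMZ for a patient in an arm meant to show what TG02 does alone. Section 1.1 lists TMZ rechallenge among the main options after first-line failure, so the step is not far-fetched.

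The protocol gives such a site nothing to work with. Section 5.2.1.3 gives Group C one TG02 schedule, eight doses per 28-day cycle, with no version for use with TMZ. Section 5.2.1.4 gives a TMZ dose for Group B only. The Group C dose-modification tables in 5.5.3.4 contain no action on TMZ. Section 1.3.3.2 explains that Group B omits TG02 in weeks 2 and 3 because the two drugs may have overlapping toxicities.

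There is also a question of classification. If TMZ counts as protocol treatment, PFS runs on through it. If it counts as other anti-cancer therapy, PFS is censored. NPFS and CDFS have no rule for censoring at new therapy.

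**Working it through.** **The plan's own figure.** Section 8.1.1 sets n = 45 with success at 13 or more, P0 = 20%, P1 = 40%, alpha 0.10 and beta 0.05. The exact binomial gives P(X ≥ 13 | 45, 0.20) = 0.0995 and P(X ≥ 13 | 45, 0.40) = 0.9554. The exact one-sided 90% lower bound at 13/45 is 0.2002, which excludes 20%. Allowing for dropout, 45 / 0.90 = 50. The design reproduces, and nothing below changes it.

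**When the option opens.** Cycles are 28 days (6.2.3), so 12 × 28 = 336 days from first dose. PFS and OS count from consent (7.2.2). Two readings of the gap from consent to first dose are possible:

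- Consent taken as the registration date (6.1.2), with first dose within 7 days (6.1.3.3): day 336 to 343.
- Consent within 14 days of first dose (6.1.1.2): day 336 to 350.

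I use the wider range. The ±3-day visit window in 6.2.4 can move it slightly.

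**Against the landmarks** (month = 30.44 days):

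| Landmark | Day | Option opens relative to it |
|---|---|---|
| 6 months | 182.6 | 153 to 167 days after |
| 9 months | 273.9 | 62 to 76 days after |
| 12 months | 365.25 | 15 to 29 days before |

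**Endpoint by endpoint.**

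- PFS-6, the 13-of-45 rule, NPFS-6 and OS-9 are fixed before the option opens.
- Success rate: a patient who completes 12 cycles without progression is already a success through the 6-month criterion.
- Median PFS: if PFS-6 is below 50%, the median falls before day 182.6 and cannot be affected. Both P0 and P1 meet this condition.
- OS-12: TMZ would have to change vital status within 15 to 29 days in a patient who was progression-free when it started. That is remote.
- Best response: only if a first response came after day 336.
- What remains is late safety, duration of response and the tails of PFS, OS, NPFS and CDFS.

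**How many patients could be progression-free by then.** The documents give no PFS curve shape, so this is assumption only.

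- Ceiling without any shape assumption (the 6-month number): 45 × 0.20 = 9, 45 × 0.30 = 13.5, 45 × 0.40 = 18.
- Exponential PFS, 45 × p^(t/182.6): at t = 336, 2.3, 4.9 and 8.3 for p = 0.20, 0.30 and 0.40; at t = 350, 2.1, 4.5 and 7.8.
- Weibull PFS, 45 × p^((t/182.6)^k), k from 0.8 to 1.2: from 1.3 (p = 0.20, k = 1.2, t = 350) to 10.1 (p = 0.40, k = 0.8, t = 336).

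These count patients without progression. They include patients who had already stopped for toxicity or other reasons, and they say nothing about how many would be given TMZ.

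**Group B, set side by side.** The synopsis Treatment row and section 4.2 let TMZ continue after cycle 12. Section 5.3 runs the combination to 12 cycles and extends only TG02. The synopsis Methodology row extends only TG02. Footnote 12 of the table in 6.4.2 caps TMZ at 12 cycles.

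**The case against.** The strongest reply is that this is one stray phrase in a synopsis. The same paragraph calls the treatment single-agent, the body of the protocol says TG02 only, and the Group C schedule in 6.4.3 has no TMZ row. The absence of TMZ rules for Group C then shows that TMZ was never intended there. This stands as to intent and keeps the point minor. It does not remove the contradiction, because the sentence as written still grants the permission.

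Four stronger readings are tempting, and the documents do not support them:

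- A reader might infer that the primary result is confounded by TMZ. The timing above rules that out.
- A reader might treat the patient counts as the number exposed to TMZ. Uptake is not given and could be zero.
- A reader might take the reference to 5.5.3.4 in 5.5.2, or the TG02 and TMZ diary line in 5.2.1.4, as signs that TMZ was planned for Group C. The first also cites the Group A section and the second stands under instructions for all groups, so both look like loose shared wording. Section 7.1.1 limits TMZ compliance checks to Group B.
- A reader might infer that the synopsis defeats the prohibition in 5.6.1 because that text ends with "other treatments not part of protocol-specified anti-cancer therapy". That is arguable at most: chemotherapy is named outright, and the closing words may qualify only the last item in the list.

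On Group B, footnote 12 may describe only the planned 12-cycle course, before any discretionary continuation. Even so, 5.3 and the Methodology row still differ from 4.2.

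**Conclusion.** The Group C synopsis sentence is wrong as written and should be corrected; the point is minor. That it was carried over from Group B is an inference, well supported by the matching wording and by the fact that Group C has no TMZ to continue. The practical risk is a site acting on the synopsis and giving an unplanned combination with no Group C schedule or dose rule.

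The statistical reach is small. It is confined to late safety, duration of response and the tails of PFS, OS, NPFS and CDFS in the few patients still on treatment about 336 to 350 days after consent. The statement on median PFS assumes PFS-6 below 50%. The timing assumes 28-day cycles given on schedule. The Group B inconsistency is separate and editorial.

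**What to change.** In the Group C paragraph of the synopsis Treatment row, drop the TMZ combination and its single-agent alternative, so that the sentence names TG02 alone as in 4.3. No change to 7.2.2 is then needed.

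Separately, the sponsor should decide whether Group B may continue TMZ after cycle 12 and then check all five places against that decision: the synopsis Methodology row, the Group B paragraph of the Treatment row, section 4.2, section 5.3 and footnote 12 of 6.4.2. Aligning the footnote with 4.2 and the synopsis Treatment row alone could leave 5.3 and the Methodology row in conflict.

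The cost is wording only: one Group C phrase, plus whichever Group B sentences need to change. No data, sample size or analysis changes.

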1.2 Development of CDK inhibitors in cancer treatment

The first generation of CDK inhibitors were non-selective, pan CDK blocking agents that showed lack of anti-tumor activity, coupled with excessive toxicity due the narrow therapeutic window (Ref. 28). Further clinical development of both alvocidib and seliciclib was abandoned as high rates of treatment induced neutropenia coupled with modest antitumor activity was observed in the conducted phase II trials (Ref. 17, Ref. 13). However several second generation CDK inhibitors (mainly those blocking CDK 4/6) have been successfully tested in metastatic breast cancer rendering again these agents eligible for further clinical development in oncology (Ref. 21).

1.3 Investigational product: zotiracilib (TG02)

1.3.1 Mechanism and Rationale

TG02, also known as zotiracilib, is an oral multi-kinase inhibitor that potently inhibits cyclin-dependent kinase (CDK) 9 but also other CDK such as 1, 2, 5 and 7 and other tyrosine kinases. Through the inhibition of CDK9, its main target, TG02 blocks the activity of RNA polymerase II, leading to a depletion of gene products with short half-lives, such as the C-MYC oncogene as well as MCL-1, a survival protein of the BCL-2 family, with the potential consequence of apoptosis induction in glioma cells.

Both MYC and MCL-1 overexpression are associated with poorer survival in ovarian and probably hepatocellular cancer, although no such data are available for GBM yet. MYC overexpression has been reported in more than 80% of GBMs (Ref. 5, Ref. 8), and MCL-1 overexpression is present in 46% (Ref. 30). The roles of MYC and MCL-1 have been explored in glial tumors only recently. MYC inhibition has been validated as a therapeutic approach in experimental glioma models in vitro and in vivo by reduced proliferation, increased apoptosis and ineffective mitosis (Ref. 1).

CDK5 is also overexpressed in a large number of GBMs (Ref. 4, Ref. 42). CDK5 is an atypical CDK, which suppresses the cell cycle without the use of its kinase activity (Ref. 43). CDK5 also regulates the phosphatidylinositol 3 (PI3)-kinase enhancer (PIKE)-A-Akt pathway and promotes GBM cell migration and invasion by phosphorylation of phosphatidylinositol 3-kinase enhancer-A GTPase (Ref. 15).

Other main CDK targets of TG02, such as CDK1 and CDK2 directly promote cell cycle progression (Ref. 44). CDK7, which represents a minor target of TG02, is also involved in the regulation of transcription (Ref. 44).

Preclinical studies of TG02 in patient-derived glioma cell lines as well as standard glioma cell lines have demonstrated broad anti-tumor activity with IC_{50} values in the range of 25-70 nM. In addition, TG02 has demonstrated activity in cell lines without MGMT promoter methylation as well as glioma stem cell lines overexpressing the MYC oncogene (see TG02 investigator brochure).

1.3.2 Clinical experience with TG02

To date, 112 patients have been treated with single agent TG02:

- TG02 was administered to 55 patients with acute leukemia at doses from 10 mg to 150 mg. The most frequently-reported TEAEs ($\geq 20\%$) were nausea, vomiting, fatigue, abdominal pain, decreased appetite, and diarrhea.
- TG02 was administered to 18 patients with multiple myeloma at doses from 50 mg to 200 mg. The most frequently-reported TEAEs ($\geq 20\%$) were diarrhea, fatigue, nausea, constipation, vomiting, hypophosphatemia, decreased appetite, and hypokalemia.
- TG02 was administered to 16 patients with chronic lymphocytic leukemia at doses from 70 mg to 150 mg. The most frequently-reported TEAEs ($\geq 20\%$) were nausea, diarrhea, vomiting, constipation, fatigue, dyspnea, cough, hyperglycemia, hypertension, anemia, decreased platelet count, dizziness, myalgia, and peripheral edema.
- TG02 was administered to 17 patients with GBM or AA at a dose of 200 mg. The most frequently reported AEs ($\geq 20\%$) were increased ALT, diarrhea, nausea, decreased neutrophil count, decreased WBC count, fatigue, vomiting, and constipation.
- TG02 was administered to 6 patients with GBM/ AA at a dose of 250 mg. The most frequently reported AEs ($\geq 20\%$) were diarrhea, fatigue, increased ALT, vomiting, decreased neutrophil count, decreased platelet count, and decreased WBC count

To date, 69 patients have been treated with TG02 in combination:

- TG02 was administered in combination with carfilzomib to 26 patients with multiple myeloma at doses from 150 mg to 300 mg. The most frequently-reported TEAEs ($\geq 20\%$) were diarrhea, nausea, vomiting, fatigue, anemia, increased ALT, decreased appetite, neutropenia, and thrombocytopenia.
- TG02 was administered in combination with dose dense TMZ to 19 patients with GBM or AA at doses from 200 mg to 300 mg. The most frequently reported TEAEs ($\geq 20\%$) were decreased lymphocyte count, decreased neutrophil count, decreased WBC count, and increased ALT.
- TG02 was administered in combination with metronomic TMZ to 21 patients with GBM or AA at doses from 200 to 250 mg. The most frequently reported TEAEs ($\geq 20\%$) were decreased lymphocyte count, decreased neutrophil count, decreased WBC count, and hypophosphatemia.
- TG02 was administered in combination with radiation therapy to 3 patients with GBM or AA at a dose of 200 mg. The most frequently reported AEs ($\geq 20\%$) were decreased lymphocyte count, urinary tract infection, increased ALT, decreased lymphocyte count, decreased neutrophil count, decreased WBC count, increased alanine aminotransferase, and hyperglycemia.

Please see the Investigator's Brochure for additional information

1.3.3 Dose and schedule rationale

1.3.3.1 Rationale for Bi-weekly Dosing of TG02

[figure not shown]
Single agent TG02 has been orally administered to 89 hematological patients at doses ranging from 10 mg to 200 mg on daily and intermittent schedules as described below. All schedules were conducted in a 28-day cycle.

- 1) daily for 28 days
- 2) 5 days on/ 2 days off for 2 weeks
- 3) Three times a week (TIW) for 3 weeks (Days 1, 3, 5, 8, 10, 12, 15, 17, 19)
- 4) Twice a week (BIW) for 4 weeks (Days 1, 4, 8, 11, 15, 18, 22 and 25)
- 5) Twice a week for 3 weeks (Days 1, 4, 8, 11, 15 and 18)

Pharmacokinetic (PK) data in patients demonstrated that T_{max} for TG02 is around 1-4 hours and $t_{1/2}$ is between 10 and 15 hours. This PK profile was not predicted by the 28-day repeat dose toxicity studies in mice and dogs. The long half-life in patients led to accumulation when TG02 was taken on multiple consecutive days (on Schedules 1 and 2, above). A TIW schedule (Schedule 3 above) reduced but did not alleviate accumulation; therefore, BIW Schedules 4 and 5 were evaluated. The PK data demonstrated that the BIW dosing schedules alleviated accumulation.

Preclinical in vitro and in vivo studies have demonstrated that daily administration is not required for the therapeutic effect. In vitro pharmacodynamics demonstrated that a single dose of TG02 resulted in significant inhibition of downstream targets for at least 24 hours with apoptosis still increasing at 24 hours (Figure 1).

[figure not shown]
Figure 1: TG02 Depletes Survival Proteins

An in vivo efficacy study was performed to determine the effects of two dosing schedules on efficacy using the MV4-11 xenograft model. Mice were dosed with TG02 either at 30 mg/kg daily for 3 weeks (for a total weekly dose of 210 mg/kg) or 60 mg/kg every 4 days for 6 doses (for a total weekly dose of 120 mg/kg). Figure 2 demonstrates that the twice weekly schedule had equivalent efficacy to the daily schedule even with a lower overall dose per week. When these schedules were compared in other tumor models, equivalent or superior efficacy was also demonstrated on the twice weekly schedule. While both

schedules were active, twice weekly dosing was generally better tolerated and therapeutically superior in several models. Therefore, this dosing regimen was used going forward and is currently used in clinical studies.

Figure 2: Efficacy of TG02 in MV4-11 tumor xenografts

